#### **4.7.4 Exploratory Efficacy Variable**

Exploratory efficacy endpoint is fever episode. Fever episode is defined as TEAEs with preferred term “Pyrexia”. Incidence of fever episode per subject during the 12-month study observation period, will be analyzed by infusion schedule and overall based on ITT, ITT2, and PP populations. Incidence rate and one-sided 99% upper confidence limit will be estimated by the primary efficacy analysis method, generalized linear models for Poisson regression with over-dispersion. The total duration of fever episode for each subject will be calculated and converted to a figure per year. These data will be presented using the standard set of summary statistics (except that the mean and SD will be calculated weighting for the duration of data available for each subject).

A by-subject listing of the fever episode will be provided.

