## 2.3 Primary Safety Endpoint/Variable

- The proportion of infusions with temporally associated AEs that occur during or within 1 hour, 24 hours, and 72 hours following an infusion of investigational product (including AEs that were determined to be unrelated to the product).

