## 4.7 Efficacy Evaluation

### 4.7.1 Analysis and Data Conventions

Confidence intervals will be calculated at the two-sided 95% level of confidence except for the primary efficacy and safety endpoints which will be one-sided 99% and 95% respectively.

This study is designed to test for non-inferiority of GC5107 which will be compared with historically-based standards. The null hypothesis is that the incidence of serious acute bacterial infections in subjects treated with GC5107 is greater than or equal to 1.0 per subject per year. The alternative hypothesis is that the incidence of serious acute bacterial infections is less than 1.0 per subject per year. Symbolically, this is expressed as follows:

H0: average incidence of serious acute bacterial infections on GC5107  $\geq$  1.0 per subject per year

H1: average incidence of serious acute bacterial infections on GC5107  $<$  1.0 per subject per year

A one-sided test based on a generalized linear models procedure for Poisson regression with  $\alpha=0.01$  will be used to test this hypothesis. Equivalently, the upper one-sided 99% confidence limit would be less than 1.0.

Adverse Event related efficacy endpoint are defined based on treatment emergency adverse event (TEAE) only, including acute serious bacterial infections, infection other than acute serious bacterial infections, incidence of infections, duration of infections, time to resolution of infection.

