### 4.7.3 Secondary Efficacy Variables

Secondary efficacy endpoints are:

- The incidence of infections other than acute serious bacterial infections meeting FDA guidance criteria.
- The number of days missed from work/school/kindergarten/day care or days unable to perform normal daily activities due to infections.
- The number of days that the care provider of the pediatric subject had to miss work in order to care for the child due to infections.
- The number of days of unscheduled physician visits due to infections.
- The number of days of hospitalizations due to infections.
- The number of days of IV therapeutic antibiotics.
- The number of days of oral (PO) therapeutic antibiotics.
- Time to resolution of infections.
- The incidence of infections other than serious bacterial infections by trough IgG levels. The categories of trough IgG levels will be determined by looking at the distribution of trough IgG levels at the study completion. Incidence will be summarized by total group mean of trough IgG level throughout treatment, including the trough IgG level from infusion 1 to follow up assessment ( $<$  mean Trough IgG,  $\geq$  mean Trough IgG).

These endpoints will be analyzed descriptively by infusion schedule and overall based on ITT and PP populations, respectively. Subject with no experience of specific event will be included in the analysis as zero incidence, zero day, or zero time duration. For hospitalizations, the number and (total) duration for each subject will be calculated and converted to a figure per year. These data will be presented using the standard set of summary statistics (except that the mean and SD will be calculated weighting for the duration of data available for each subject).

Infections is defined as TEAE coded to MedDRA system organ class ‘Infections and infestations’, or otherwise suggestive of an infection by medical review.

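### The exploratory efficacy endpoint of fever counts every Pyrexia TEAE, so infusion-reaction fevers enter a rate labelled efficacy; a breakdown by onset with matched follow-up time would make it readable

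*SAP*

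**What the plan says.** SAP 4.7.4 gives the variable its status, "Exploratory efficacy endpoint is fever episode", and its definition, "Fever episode is defined as TEAEs with preferred term" Pyrexia. Nothing further in that section narrows the count by onset, causality or the presence of an infection.

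The count is then used in two ways. "Incidence rate and one-sided 99% upper confidence limit will be estimated by the primary efficacy analysis method", that is, by the over-dispersed Poisson model, in the ITT, ITT2 and PP populations, by infusion schedule and overall. In addition, "The total duration of fever episode for each subject will be calculated and converted to a figure per year". A by-subject listing is planned. No threshold or success rule is attached to fever.

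Two other places matter:

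- SAP 2.3 bases the primary safety endpoint on "temporally associated AEs that occur during or within 1 hour, 24 hours, and 72 hours following an infusion", whatever their judged cause.
- SAP 4.7.3 ties several neighbouring efficacy variables to infection, for example "The number of days of hospitalizations due to infections". It defines an infection by MedDRA system organ class "or otherwise suggestive of an infection by medical review". The fever definition has no such link.

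The revision history shows that 4.7.4 came in with SAP version 4.0. Fever is not among the efficacy endpoints in the protocol synopsis, so no rationale is available there.

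**The concern.** Fever in a subject on immunoglobulin replacement can mean at least two things: an infection that replacement did not prevent, or a reaction to the infusion. Only the first bears on efficacy. SAP 4.7.4 puts both into one rate under an efficacy label, and into the annualised duration as well. A reader of the report could not tell from that rate how much reflects tolerability.

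The by-schedule presentation adds to the difficulty. Subjects on the 21-day schedule receive 17 infusions and those on the 28-day schedule 13. With the same risk per infusion and the same protection against infection, the 21-day group would still show the higher rate.

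What is at stake is the interpretation of one exploratory result. No trial decision depends on it.

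**Working it through.** The plan states no fever rate, power or threshold, so there is no figure of its own to reproduce.

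**Inputs from the documents**

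- Infusions per subject, m: 48/4 + 1 = 13 (28-day) and 48/3 + 1 = 17 (21-day), matching the infusion numbers in SAP 2.6 and SAP Table 1.
- Follow-up per completer, T, from the formula in SAP 4.7.2 with the follow-up visit at week 52 or 51: (364 + 1)/365.25 = 0.999 years and (357 + 1)/365.25 = 0.980 years.
- N = 42, the minimum in the protocol synopsis (26 + 8 + 8).

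**Assumed inputs (not in the documents)**

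- q: probability that an infusion is followed by an infusion-related pyrexia.
- b: rate of pyrexia from all other causes, per subject-year.

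**Step 1: added rate and share.** Added rate = m·q/T. Share of all counted fevers = (m·q/T)/(m·q/T + b). Each cell gives 28-day / 21-day.

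| q | Added per subject-year | Share, b = 0.1 | Share, b = 0.25 | Share, b = 1.0 |
|---|---|---|---|---|
| 0.5% | 0.065 / 0.087 | 39% / 46% | 21% / 26% | 6% / 8% |
| 1% | 0.13 / 0.17 | 57% / 63% | 34% / 41% | 12% / 15% |
| 2% | 0.26 / 0.35 | 72% / 78% | 51% / 58% | 21% / 26% |
| 3% | 0.39 / 0.52 | 80% / 84% | 61% / 68% | 28% / 34% |
| 10% | 1.30 / 1.73 | 93% / 95% | 84% / 87% | 57% / 63% |

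The share reaches one half at q = b·T/m. For b = 0.25 that is 1.9% / 1.4%; for b = 1.0 it is 7.7% / 5.8%.

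**Step 2: effect on the reported limit.** Take b = 0.25, N = 42 all on one schedule, no over-dispersion, and a log-link Wald limit, rate × exp(2.326/√events).

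- q = 0: rate 0.25, limit 0.51 / 0.52.
- q = 2%, 28-day: events = 0.25 × 42 × 0.999 + 42 × 13 × 0.02 = 21.4; rate 0.51; limit 0.84.
- q = 2%, 21-day: events = 0.25 × 42 × 0.980 + 42 × 17 × 0.02 = 24.6; rate 0.60; limit 0.95.

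**Step 3: schedule effect.** For equal q, the added rates are in the ratio (17/0.980)/(13/0.999) = 1.33. In the example the total rates are 0.60 and 0.51, although b and q are the same on both schedules.

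**Step 4: the denominator for a split.** Ignoring infusion duration, the 72-hour windows cover 13 × 3/365 = 10.7% of follow-up (28-day) and 17 × 3/358 = 14.2% (21-day). If fevers in the windows were dropped but that time kept, a true outside rate of 0.25 would be reported as 0.25 × 0.893 = 0.22 or 0.25 × 0.858 = 0.21. That is too low, and in the product's favour.

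With matched time, and if all infusion-related fevers start within 72 hours, the outside row estimates b = 0.25 on both schedules. The inside row estimates b + q × 365.25/3 = 0.25 + 0.02 × 121.75 = 2.69 per year of window time, also on both schedules. The schedule difference in Step 3 disappears.

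**The case against.** The strongest reply is that nothing depends on this endpoint. It is exploratory and has no success rule. The limit of 1.0 per subject per year is stated only for acute serious bacterial infections, so a reader who held the fever limit against 1.0 would be applying a criterion that the SAP does not set. In a single-arm trial, extra fevers can only raise the rate, so the all-events count is conservative. All of this stands, and it caps the severity.

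A reader might also call it an error that one event counts as both safety and efficacy. The documents do not support that. SAP 2.3 deliberately includes AEs judged unrelated to the product, and SAP 4.7.1 puts the AE-based efficacy endpoints on TEAEs, "including acute serious bacterial infections, infection other than acute serious bacterial infections, incidence of infections, duration of infections, time to resolution of infection". A pneumonia starting within 72 hours of an infusion would also count on both sides. The endpoints are analysed separately, so nothing is inflated. The difficulty is the meaning of the fever rate, not the overlap.

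Some separating information is already planned: the fever listing, and AE summaries by the 1, 24 and 72-hour windows and by suspected relation (SAP 2.4). I did not have the text of SAP 4.8.3 or of protocol section 8. The absence of a split is therefore a statement about SAP 4.7.4, not about the whole plan. Even so, a listing and general AE tables do not give a fever rate by timing.

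Finally, timing is not causality: an infectious fever can start within 72 hours of an infusion. That is a good reason to keep the total as the main figure.

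**Conclusion.** The point holds as a matter of definition. Followed as written, SAP 4.7.4 counts infusion-reaction fevers in a rate, a 99% limit and a duration that are labelled efficacy. At an assumed 1% to 3% of infusions, the addition is about 0.13 to 0.39 episodes per subject-year (28-day) or 0.17 to 0.52 (21-day). The direction is against the product, the schedules can differ through infusion count alone, and the primary conclusion is untouched.

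Two stronger readings are tempting and should not be drawn. One is that infusion reactions dominate the fever rate. Across the assumed values of q and b the share runs from 6% to 95%, and the documents give neither input, so domination is possible but not shown. The other is that fever accompanying a reported infection is coded only as the infection, leaving infusion reactions over-represented. That depends on AE recording rules that I could not check.

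This is a cheap improvement; severity is nice to have.

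**What to change.** In SAP 4.7.4:

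- Keep the rate of all Pyrexia TEAEs, with its one-sided 99% limit, as the main figure.
- Add a supplementary breakdown by onset: during or within 72 hours after an infusion, and outside that window.
- Calculate each row's rate on the follow-up time inside or outside the windows only, by schedule and overall. For subjects who withdraw, end the last window at withdrawal.
- Split the annualised fever duration in the same way, classifying each episode by its onset.
- State that the outside-window row is the one to read for efficacy.

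The cost is SAP wording and a little programming; onset relative to infusion is already needed for the primary safety endpoint. The downside is that an infectious fever starting within 72 hours falls in the peri-infusion row, though it stays visible in the total.

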### **4.8 Safety Evaluation**

All safety endpoints will be summarized by infusion schedule and overall based upon the ITT population as defined in Section 4.4.

#### **4.8.1 Primary Safety Endpoint**

The primary safety endpoint will be analyzed with the objective of demonstrating that the percentage of infusions with one or more infusion-related AE is less than 40% [3]. In order to estimate the overall probability of the occurrence of an AE possibly related to infusion for study subjects, as well as a one-sided 95% upper confidence bound, the Generalized Estimating Equation (GEE) method of Zeger and Liang [7] will be used. The response variable will be defined as the logit of the probability of an AE associated with an infusion, and the overall probability and the confidence bound will be estimated under a model with a compound symmetry working correlation structure. This approach allows the outcome of having an AE associated with an infusion to be correlated across infusions within individuals. A demonstration of adequate safety requires that the one-sided 95% upper confidence bound of the probability that an infusion is associated with an AE is below 0.40.

All abnormal laboratory data assessed during the study including the data assessed at Final Visit (Follow-up) will be listed on an individual basis as actual values at each visit as well as the change from baseline and analyzed similarly. In addition, shift tables will be used to show the laboratory parameter deviations with respect to the normal ranges of laboratory values from baseline to each post-dose Visit, respectively (i.e. “Normal” vs. “Low” or “High”, respectively).

By-subject listings of all laboratory data and abnormal laboratory data will be provided separately by treatment group, with abnormal values highlighted (not needed if for listing of abnormal laboratory data), and including center, subject identifier, age, sex, race, ethnicity, weight and visit. Laboratory reference ranges should also be listed.

Viral safety data and DAT/Coombs test will be listed and summarized by planned visit. Table 2 below summarizes the viral safety test at screening and during study. Changes from baseline in viral safety test will be summarized using shift tables where appropriate.

Table 2. Viral Safety Assessment

Category	At Screening	At other following visits
HBV serology	HBs Ag, anti-HBs Ab, anti-H Bc Ab	HBs Ag
HBV NAT	HBV DNA	HBV DNA
HCV serology	Total anti-HCV Ab	
HCV NAT	HCV RNA	HCV RNA
HAV serology	Total anti-HAV Ab	
HAV NAT	HAV PCR	HAV PCR
HIV serology	HIV Ab	
HIV NAT	HIV-1 RNA	HIV-1 RNA
Parvovirus B19 IgG	Parvovirus B19 IgG	
Parvovirus B19 IgG DNA	Parvovirus B19 IgG DNA	Parvovirus B19 IgG DNA

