	
15. Subject is receiving the following medication:
 
 
• Corticosteroids (oral or parenteral daily dose of <math>\geq 0.15</math> mg/kg/day of prednisone or equivalent).
 
• Other immunosuppressive drugs or chemotherapy.
 
 
16. Females who are pregnant, breast feeding or planning a pregnancy during the study. Women who become pregnant during the study will be withdrawn from the study. Males who do not agree to use contraception will not qualify to be enrolled in the study. Males are not allowed to donate sperm during the study.
 
17. Subject has participated in another clinical study within 3 weeks prior to study enrollment.

EFFICACY ENDPOINT
	
1) Primary Efficacy Endpoint: The incidence of acute serious bacterial infections meeting Food and Drug Administration (FDA) guidance criteria (bacterial pneumonia, bacteremia/sepsis, bacterial meningitis, visceral abscess, osteomyelitis/septic arthritis).
 
2) Secondary Efficacy Endpoints
 
 
• The incidence of infections other than acute serious bacterial infections meeting FDA guidance criteria.
 
• The number of days missed from work/school/kindergarten/daycare, or days unable to perform normal daily activities due to infections.
 
• The number of days that the care provider of the pediatric subject had to miss work in order to care for the child due to infections.
 
• The number days of unscheduled physician visits due to infections.
 
• The number of days of hospitalizations due to infections.
 
• The number of days of intravenous (IV) therapeutic antibiotics.
 
• The number of days of oral therapeutic antibiotics.
 
• Time to resolution of infections.
 
• The incidence of infections other than serious bacterial infections by trough IgG levels.
 

SAFETY ENDPOINTS
	
1) Primary Safety Endpoint: The proportion of infusions with temporally associated adverse events

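### SAP 4.8.1 describes the primary safety numerator in causality terms, while the endpoint definition counts all temporally associated AEs, including unrelated ones

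*SAP*

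**What the plan says.** **Endpoint definition.** SAP 2.3 gives the variable as "The proportion of infusions with temporally associated AEs that occur during or within 1 hour, 24 hours, and 72 hours following an infusion", and adds the qualifier "including AEs that were determined to be unrelated to the product". The protocol synopsis defines it the same way, starting "The proportion of infusions with temporally associated adverse events" and carrying the same qualifier.

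**Target.** SAP 4.8.1 states the objective as showing that "the percentage of infusions with one or more infusion-related AE is less than 40" percent. The synopsis paragraph on statistical method uses the same wording.

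**Estimation.** SAP 4.8.1 introduces the GEE analysis with "In order to estimate the overall probability of the occurrence of an AE possibly related to infusion for study subjects".

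**Model and pass rule.** The same paragraph then says "The response variable will be defined as the logit of the probability of an AE associated with an infusion", explains that "This approach allows the outcome of having an AE associated with an infusion to be correlated across infusions within individuals", and requires that "the one-sided 95% upper confidence bound of the probability that an infusion is associated with an AE is below 0.40".

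**The concern.** One primary criterion is described with three event terms: *infusion-related*, *possibly related to infusion* and *associated with*. Only the last fits the endpoint definition, which is indifferent to causality. The other two can be read as a causality filter. *Possibly related* is especially exposed, because SAP 2.4 uses almost the same phrase for suspected adverse reactions, a separate secondary endpoint.

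The wording fixes the numerator of a formal pass/fail rule. The same variable also feeds the ITT2 sensitivity analysis (SAP 4.4 and 4.11) and the subgroup summaries (SAP 4.7.1.6). A related-only numerator is a subset of the defined one, so any error runs in the direction that favours passing. It would also make the result depend on causality judgements in an open-label, single-arm trial, a dependence that the endpoint as defined avoids.

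**Working it through.** **Comparison of the texts**

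| Place | Event term | Are unrelated AEs counted? |
|---|---|---|
| Synopsis, primary safety endpoint | temporally associated | yes, expressly |
| SAP 2.3 | temporally associated | yes, expressly |
| Synopsis, statistical method | infusion-related | not stated; can be read as no |
| SAP 4.8.1, objective | infusion-related | not stated; can be read as no |
| SAP 4.8.1, estimation sentence | possibly related to infusion | not stated; most naturally no |
| SAP 4.8.1, response, correlation sentence, pass rule | associated with | not stated; fits SAP 2.3 |

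No text we could see defines one of these terms by another.

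**Could it change the verdict?** The text supplied gives no expected AE rate or power figure for this endpoint, so there is no plan figure to reproduce. What follows is conditional.

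Inputs from the documents:
- N = 42 to 50 subjects (synopsis).
- m = 13 infusions on the 28-day schedule or 17 on the 21-day schedule (SAP Table 1). Total: 42 × 13 = 546 to 50 × 17 = 850.
- One-sided 95% upper bound (SAP 4.7.1 and 4.8.1), z = 1.645, limit 0.40.

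Assumptions: within-subject correlation (ICC) 0 to 0.5, the AE proportions, and the share of AE-positive infusions that a related-only count would keep.

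Approximation to the planned compound-symmetry GEE:

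- n_eff = N·m / (1 + (m − 1)·ICC)
- upper bound = expit( logit(p) + 1.645 / √(n_eff·p·(1 − p)) )

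*Largest passing counts.* With N = 42, m = 13 and ICC 0.5, n_eff = 546/7 = 78. At 168/546 (p = 0.3077) the bound is expit(−0.811 + 0.404) = 0.3995, which passes; 169/546 gives 0.401 and fails. With N = 50, m = 17 and ICC 0, n_eff = 850. At 316/850 (p = 0.3718) the bound is expit(−0.525 + 0.117) = 0.399, which passes; 317/850 gives 0.401 and fails. The passing threshold therefore runs from 30.8% to 37.2%.

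*Bounds at given observed proportions, over the same range:*

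| Observed proportion | Upper bound | Result |
|---|---|---|
| 0.28 | 0.306–0.371 | pass |
| 0.30 | 0.326–0.392 | pass |
| 0.40 | 0.428–0.494 | fail |
| 0.45 | 0.478–0.543 | fail |

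An observed 40% becomes a pass if the share kept is below threshold/0.40, that is 0.308/0.40 = 0.77 to 0.372/0.40 = 0.93. For example, keeping 70% gives 0.28, which passes throughout.

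*Simulation.* Settings: 10,000 trials each; (N, m) = (42, 13) and (50, 17); ICC 0, 0.1, 0.3 and 0.5 (beta-binomial); intercept-only exchangeable logit GEE with robust variance. Each AE-positive infusion was kept as related at random with probability 0.8 or 0.6.

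| True all-causality proportion | Endpoint as defined passes | Related-only passes, 80% kept | Related-only passes, 60% kept |
|---|---|---|---|
| 0.40 | 5.0–5.7% | 51.1–99.9% | 99.5–100% |
| 0.45 | 0–0.7% | 20.8–77.4% | 95.8–100% |

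At lower true proportions, over both shares, the two verdicts differ in at most 0.1% of trials at 0.15, at most 1.6% at 0.20, 0–13% at 0.25, 0–43% at 0.30 and 8–78% at 0.35. The 43% at 0.30 arises at ICC 0.5; at ICC 0 to 0.1 the figure there is about 5% or less.

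**The case against.** The strongest reply is that this is loose wording, already settled by the operative text. The response variable and the pass rule carry no causality filter. The objective sentence refers back to the primary safety endpoint, which SAP 2.3 defines with an explicit inclusion of unrelated AEs. Where the SAP clearly means causality, it ties it to GC5107 or the investigational product (SAP 2.4), not to the infusion. SAP 4.11 records no narrowing of the numerator, which suggests that none was intended. Protocol 9.1.7 and SAP 4.8.3 were not available to us. The revision history says that version 3.0 clarified the AEs within 1, 24 and 72 hours, so a linking definition may exist. Finally, reversals are common only when the true rate is near or above 0.35 or the correlation is high, and no figure in the supplied documents points to either.

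Much of this stands. Read as a whole, the plan favours the all-causality count, and the effect on the verdict is conditional. It does not remove the conflict. The sentence naming the quantity to be estimated says *possibly related*, and following it literally gives a numerator that the endpoint definition excludes. A definition elsewhere would still leave contradictory words in the section that sets the pass rule. The silence of SAP 4.11 also means that a related-only analysis would be an undocumented departure.

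**Conclusion.** The concern holds. The objective and estimation sentences of SAP 4.8.1, and the matching synopsis sentence, conflict with the endpoint definition on which AEs count. This is a contradiction within a primary criterion, not merely missing detail, and it should be fixed.

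The verdict changes only if the observed all-causality proportion lies above the passing threshold (30.8% to 37.2%, for 546 to 850 infusions and ICC 0 to 0.5) and the related-only proportion lies at or below it. At a true proportion of 0.20 or less the choice almost never matters. At 0.40 the endpoint as defined passes in about 5% of trials, against 51% to 100% for a related-only count that keeps 80% or 60% of AE-positive infusions. The subject and infusion numbers are the plan's; the correlation, AE rates and shares kept are assumptions. How likely a reversal is cannot be stated from the supplied text.

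No conclusion is drawn about which time window the 0.40 bound applies to, because parts of SAP 4.8 and protocol 9.1.7 were not available.

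**What to change.** Replace *infusion-related AE* and *AE possibly related to infusion* with *temporally associated AE regardless of causality* in the synopsis method sentence, throughout SAP 4.8.1, and wherever the wording recurs (protocol 9.1.7 should be checked). Use the same term for the GEE response and the pass rule. If the protocol can no longer be changed, record the clarification in SAP 4.11. Keep product-related AEs as the secondary endpoints of SAP 2.4. The sponsor should also confirm that 4.8.1 names, or cross-refers to, the time window to which the bound applies.

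The cost is one SAP paragraph and one synopsis sentence, plus any recurrences. No new data are needed. The downside is that the margin to 0.40 may be smaller than with a related-only count.
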